#### Treatment

1=Ofatumumab

0=No further treatment

#### Response at Study Entry

1=CR

0=PR

#### Number of Induction Therapies

1=3 Therapies

0=2 Therapies

#### Type of Prior Treatment

2=Chemoimmunotherapy

1=Only alkylating therapy

0=Other

## Age

1=  $\geq 70$ 0=  $< 70$ 

## Gender

1=Female

0=Male

## Race

1=White

0=Non-white

## Modified RAI Stage

2=High Risk (stage III, IV)

1=Intermediate Risk (stage I, II)

0=Low Risk (Stage 0)

## Binet Stage

2=C

1=B

0=A

## MRD Status

1=Positive

0=Negative

## Cytogenetics (FISH)

3= 17p-

2= 11q-

1= 6q- or 12q or 13q-

0= no aberration

Note the following rules to define an aberration using 20% as a cut-off. The same rules will also be repeated using a cut-off of 12%.

cytogenetics $\geq 20\%$  = YES vs. cytogenetics  $< 20\%$  = NO for aberrations (12% will also be used as a cut-off)

17p- [a] vs. 11q- [b] vs. 6q- or +12q or 13q- [c] vs no aberration [d]

[a] All subjects that have  $\geq 20\%$  for 17p-, disregarding the presence of any other aberrations.

[b] All subjects that have  $\geq 20\%$  for 11q-, absence of 17p-, disregarding the presence of any other aberrations.

[c] All subjects that have  $\geq 20\%$  for 6q- or +12q or 13q-, absence of 17p- or 11q.

[d] Subjects with no aberration (or less than 20% of cells).

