6.2. Efficacy

6.2.1. Definition of Response

While subjects will be entering the study in remission, changes in status to disease progression or even from PR to CR will be determined according to the definitions of response in the IWCLL updated NCI-WG guidelines [Hallek, 2008] and documented at visits outlined in the time and events table. For a tabular summary of all criteria of response definition in CLL patients see Appendix 2. The IWCLL updated NCI-WG guidelines should be applied in the context of clinical judgment and determination of disease progression is at the physician's discretion.

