6.2.1.1. Complete Remission (CR)

CR requires all of the following criteria as assessed at least 2 months after therapy or at the earliest 2 months after beginning this maintenance protocol (i.e. ofatumumab treatment/observation):

Peripheral blood lymphocytes (evaluated by blood and differential count) below 4×10^9 (4000/ μ L)

Absence of significant lymphadenopathy (e.g. lymph nodes > 1.5 cm diameter).

No hepatomegaly or splenomegaly.

Absence of constitutional symptoms

Blood counts above the following values:

- a. Neutrophils > 1.5×10^9 /L*
- b. Platelets > 100×10^9 /L*
- c. Hemoglobin > 11.0 g/dL (6.8mmol/L)**

*without need for exogenous growth factors

**without red blood cell transfusion or need for exogenous erythropoietin

Bone marrow aspirate and biopsy should be performed at least 2 months after the final treatment and if clinical and laboratory results listed above in Section 6.2.1.1 (items 1 to 5) demonstrated that a CR has been achieved. The marrow sample should be analyzed by flow cytometry to demonstrate that the marrow is free of clonal CLL cells. Cases with residual CLL cells by conventional flow cytometry are defined as PR.

To define a CR, the marrow sample must be at least normocellular for age, with less than 30% of nucleated cells being lymphocytes. Lymphoid nodules should be absent. If lymphoid nodules can be found, immunohistochemistry analysis should be performed to assess if nodules are comprised primarily of T-cells or lymphocytes

other than CLL cells or of CLL cells. If marrow is hypocellular, repeat after 4-6 weeks, provided the blood counts have recovered (as defined in Section 6.2.1.1 item 5). Marrow biopsies should be compared with any pretreatment marrow. In some cases, it is necessary to postpone the marrow biopsy until after all other criteria to define a CR have been satisfied, however, this time interval should not exceed 6 months after treatment.

Subjects who fulfill all the preceding criteria for CR (Section 6.2.1.1 items 1 to 6) but have persistent anemia, thrombocytopenia or neutropenia, apparently unrelated to CLL but related to drug toxicity, should be considered as CR with incomplete bone marrow recovery.

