6.3.1. Flow Cytometry for B-CLL Diagnosis/Confirmation of Phenotype and B-cell Monitoring

6.3.1.1. B-CLL Diagnosis/Phenotype Confirmation

The B-CLL immunophenotype will be assessed by analysis of surface expression of: CD5, CD19, CD20, CD23, CD76b, and surface Ig at screening, if possible and at relapse. If the subject is in CR, results prior to latest response may be used, if available.

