6.3.3. Prognostic Factors

Whole blood will be collected at the baseline visit, if possible, and/or upon relapse for later analysis of the following prognostic factors:

- IgV_H mutational status
- V_H3-21 usage
- Cytogenetics (by FISH) including but not limited to; 6q⁻, 11q⁻, +12q, 17p⁻, 13q⁻
- β₂ microglobulin

Analysis of these factors are performed in batches by a central laboratory. Details for procedures and shipments are provided separately.

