The final analysis of PFS will be based on a two-sided test with a significance level of 0.0498. The survival distributions will be estimated using Kaplan-Meier survival curves and will be compared using a stratified log-rank test. The Pike estimator [Berry, 1991] of the treatment hazard ratios (HR) will be provided, together with the 95% Confidence Interval (CI). The Pike estimator, which is a nonparametric estimator of the HR, has been specifically developed for survival data and is used as a measure of the relative survival experience of two groups. Within the range of values of the ratio of the hazard rates of interest in clinical trials, the Pike estimator is more efficient in terms of mean square error than the Cox proportional hazard method [Bernstein, 1981]

If there are a sufficient number of progressions or deaths, median PFS, first and third quartiles and 95% CI, will be estimated using the Brookmeyer-Crowley method [Brookmeyer, 1982]. A figure and listing of progression-free survival time will also be provided.

A supplementary table showing the details of the number at risk, number of events, and number censored with the event time will also be produced. Estimates of median PFS after 6 months, 1 year and 2 years of exposure (or observation) will also be provided.

In addition to the stratified log-rank test based on the Kaplan-Meier procedure, a Cox regression model using a stepwise procedure will be used and will include covariates for treatment, stratification factors [CR or PR at study entry; number of previous induction treatments; and type of prior treatment (chemoimmunotherapy, only alkylating monotherapy, or other treatment)] and other baseline data deemed appropriate such as age, Binet stage and baseline cytogenetics data. Treatment will remain forced in the model. An entry/removal significance level of 0.05 will be used. Analytical results will include the estimated hazard ratios along with 95% confidence intervals and associated probabilities for the effect of treatment, stratification factors, and the covariates. The hazard ratio for treatment will express the risk of experiencing disease progression or death for ‘ofatumumab maintenance’ vs ‘observation’ (i.e., no further treatment).

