#### **Disease Markers:**

- Minimal Residual Disease (MRD)

The number and percentage of subjects with positive and negative MRD will be provided at each timepoint. The proportion of subjects with negative MRD and positive MRD will be compared between treatment groups with the Cochran-Mantel-Haenszel test adjusting for stratification factors (response at entry, number of prior treatments and type of prior treatment). An analysis of the time to first MRD positivity for subjects who were MRD negative at baseline will also be provided using Kaplan-Meier methodology.

- B-cell monitoring

The change and percent change of  $CD5^+CD19^+$  and  $CD5^-CD19^+$  from baseline will be summarized to assess the treatment effect, to monitor the normal B-cell population, and to follow their recovery. In addition, frequency and percentage of subjects with complete B-cell depletion and near-complete B-cell depletion will be summarized. Complete B-cell depletion is defined as the absolute value of  $CD5^+CD19^+$  and  $CD5^-CD19^+$  both equal to zero cells/uL. Near complete B-cell depletion is defined as the sum of the absolute value of  $CD5^+CD19^+$  and  $CD5^-CD19^+$   $<5$  cells/uL.

Tables that will be provided are:

- Summary of  $CD5^+CD19^+$  counts over time
- Summary of  $CD5^-CD19^+$  counts over time
- Summary of  $CD5^+CD19^+$  change from baseline (counts and percentage)
- Summary of  $CD5^+CD19^+$  percent change from baseline (counts and percentage)
- Summary of  $CD5^-CD19^+$  change from baseline (counts and percentage)
- Summary of  $CD5^-CD19^+$  percent change from baseline (counts and percentage)
- Summary of subjects with complete B-cell depletion Summary of subjects with near-complete B-cell depletion
- Prognostic markers correlating with clinical response

Cox-regression will be used to explore the relationship between PFS and the following explanatory variables: treatment group, cytogenetics (analyzed by FISH) at baseline,

IgVH mutational status at baseline,  $\beta$ 2 microglobulin at baseline, baseline CD20 and baseline complement level. Ctau and Cmax at Cycle 1 Day 1, Cycle 1 Day 8, and Cycle 4 and cytogenetics at relapse may also be considered as possible explanatory variables in the model.

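### The FISH coding rule counts remission samples with too few leukemic cells as 'no aberration', which ties that class to CR/PR at entry

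*SAP*

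**What the plan says.** **Coding rule.** SAP 9.2.14, under Cytogenetics (FISH), sets four ranked levels: 17p-; 11q-; any of 6q-, +12q or 13q-; and level 0. Level 0 is "Subjects with no aberration (or less than 20% of cells". The SAP adds: "The same rules will also be repeated using a cut-off of 12" percent. No level exists for a sample that cannot be assessed.

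**Specimen and timing.** Protocol 6.3.3 reads: "Whole blood will be collected at the baseline visit, if possible, and/or upon relapse for later analysis of the following prognostic factors". Appendix 1 places prognostic factors at screening and at withdrawal. Protocol 6.2.1 describes the population at that time: "While subjects will be entering the study in remission". CR or PR at entry is a stratification factor.

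**Meaning of CR.** Protocol 6.2.1.1 requires: "The marrow sample should be analyzed by flow cytometry to demonstrate that the marrow is free of clonal CLL cells". Residual CLL cells on conventional flow make the subject a PR.

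**A neighbouring marker.** For the immunophenotype, protocol 6.3.1.1 provides: "If the subject is in CR, results prior to latest response may be used, if available". Section 6.3.3 gives no such allowance for FISH.

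**Use.** The stepwise PFS Cox model in SAP 11.1 takes treatment, the stratification factors and "other baseline data deemed appropriate such as age, Binet stage and baseline cytogenetics data". SAP 11.2, on prognostic markers, states "Cox-regression will be used to explore the relationship between PFS and the following explanatory variables", and baseline cytogenetics is among them. SAP 8.3 and 11.1 list cytogenetics as a PFS subgroup. Appendix 1 of the SAP for the 280-event analysis keeps safety Tables 3.1530 and 3.1540 by cytogenetics at the 20% cut-off.

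**The concern.** A FISH percentage describes the cells on the slide. In a patient with active leukemia, a low percentage is evidence that the lesion is absent. In a patient in remission it may mean only that few leukemic cells were there to score. The SAP rule gives both situations the same code.

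Protocol-defined CR subjects therefore cannot occupy levels 1 to 3, and level 0 becomes partly a marker of depth of remission. Response at entry and baseline cytogenetics are both candidates in a stepwise Cox model with a 0.05 entry/removal level, so the selection can exchange one for the other. A hazard ratio for 17p- or 11q- against level 0 is then a contrast with a mixed group, and any result reported for subjects with no aberration carries the wrong label.

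**Working it through.** The plan gives no figure for this point, so there is none to reproduce. The check compares the cut-offs with the protocol's own definitions.

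**1. Upper bound.** Observed FISH % = (leukemic share of scored cells) × (share of the clone carrying the lesion).

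Leukemic share needed to leave level 0:

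| Share of clone with lesion | 20% cut-off | 12% cut-off |
|---|---|---|
| 100% | 0.20 / 1.00 = 20% | 0.12 / 1.00 = 12% |
| 75% | 0.20 / 0.75 = 26.7% | 0.12 / 0.75 = 16% |
| 50% | 0.20 / 0.50 = 40% | 0.12 / 0.50 = 24% |

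For example, 10% leukemic cells with a wholly 17p- clone give 0.10 × 1.00 = 10%, which is level 0 at both cut-offs.

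**2. CR by blood count alone.** Take the edge of the criteria in protocol 6.2.1.1: lymphocytes 4.0 and neutrophils 1.5 × 10⁹/L, ignoring other leukocytes, a total of 5.5.

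- 20%: 0.20 × 5.5 = 1.1 × 10⁹/L clonal cells, or 1.1 / 4.0 = 27.5% of lymphocytes.
- 12%: 0.12 × 5.5 = 0.66 × 10⁹/L, or 0.66 / 4.0 = 16.5% of lymphocytes.

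The blood count alone does not exclude this many clonal cells.

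**3. CR by marrow flow.** The requirement for a marrow free of clonal cells does exclude it. For scale, protocol 6.2.3 sets MRD negativity at under 1 CLL cell per 10,000 leukocytes (0.01%). The cut-offs are 20 / 0.01 = 2000 and 12 / 0.01 = 1200 times that limit. A subject who truly meets the CR definition is level 0 at either cut-off, so repeating the rule at 12% does not help.

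**4. Illustration of size.** The documents give neither the share in CR (c) nor the share whose leukemia carries any listed aberration (p). Assume c = 10–30% and p = 50–80%, with p equal in CR and PR. Assume also that every CR subject has a numeric result and is coded 0, and that no PR carrier is missed. Then

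misplaced share of level 0 = pc / [(1 − p) + pc].

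- c = 0.10, p = 0.50: 0.05 / 0.55 = 9%.
- c = 0.20, p = 0.70: 0.14 / 0.44 = 32%.
- c = 0.30, p = 0.80: 0.24 / 0.44 = 55%.

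The width of this range shows that the documents do not fix the size.

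**The case against.** **The laboratory method is not in the documents.** Protocol 6.3.3 has FISH run in batches at a central laboratory, with procedures described elsewhere. We are not told whether all nucleated cells, mononuclear cells or enriched B cells are scored, or whether a poor sample returns a percentage or a failed test. SAP 9.1 says that answers of not evaluable are to be displayed as such, and the 280-event SAP names IgVH figures that exclude a not-available group. If the laboratory flags such samples, they need not reach level 0. This stands, and it makes the finding conditional. Enrichment could rescue some PR samples, but not a sample with no detectable clonal cells.

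**Not every labelled CR is flow-negative or sampled.** Appendix 1 says that CR may be confirmed by marrow and flow, and the baseline FISH sample is taken only if possible. A reader might infer that nearly all aberration carriers in CR are miscoded. The documents do not support that figure.

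**A second specimen exists.** FISH may also be taken at relapse, and the SAP carries cytogenetics at relapse as an optional separate variable. It would be wrong to say that FISH is never measured with active disease. But relapse results exist only for subjects who relapse, so they depend on the outcome and cannot repair a baseline covariate for PFS.

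**The reach is limited.** The 280-event SAP drops PFS Tables 2.0180–2.0183 by cytogenetics and the prognostic-marker Cox Table 2.2080. The final-analysis output list has no safety table by cytogenetics. Both later analyses are descriptive. All of this stands. The dropped tables were nevertheless interim outputs, and the interim is where the primary endpoint was met.

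**Conclusion.** The point holds as a defect in a stated derivation rule. Applied as written, SAP 9.2.14 puts subjects without a lesion and subjects with too few leukemic cells to test in one class, and that class is confounded with CR/PR at entry. This rests on FISH being scored on cells that are not enriched enough to restore the clone, and on the laboratory not withholding a percentage for inadequate samples. The size is unknown; 9% to 55% of level 0 is an illustration on assumed inputs, not an estimate.

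The affected uses are secondary or exploratory:

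- baseline cytogenetics as a candidate in the PFS Cox model;
- the interim cytogenetics subgroups and prognostic-marker model;
- any prognostic-factor forest plot that includes it (Figures 12.0120 and 12.0122 do not list their factors);
- safety Tables 3.1530 and 3.1540.

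A reader might infer that the primary result or the randomized comparison is compromised. It is not: the stratified log-rank test does not use FISH, and the class is fixed from a baseline sample, so a treatment comparison within it is still randomized. What is wrong is the description of the class and the contrast between classes. The rule should be corrected, but nothing confirmatory depends on it.

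**What to change.** In SAP 9.2.14, add a level for baseline FISH, 'not evaluable (insufficient clonal cells)'. Assign it when no lesion reaches the cut-off and the leukemic share of the scored cells is below that same cut-off (20% or 12%).

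- Use the central laboratory's evaluability flag where one exists.
- Otherwise use the screening CD5+CD19+ count divided by the denominator that matches the cells FISH scored: total leukocytes if unselected. State that denominator in the SAP, because a mismatch would move true negatives out of level 0.
- Reserve 'no aberration' for evaluable subjects.
- Show the new level separately in the Cox models, the forest plots and Tables 1.4142, 3.1530 and 3.1540.
- Tabulate baseline cytogenetics by CR/PR at entry.
- Use existing pre-induction FISH results only in a sensitivity analysis. They mix local with central methods and depend on which sites have them.

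CD5+CD19+ is not proof of clonality (protocol 6.2.3 adds light-chain analysis for that), so the ratio approximates an upper bound on the clonal share. A value below the cut-off is good evidence that FISH could not have been positive; a value above it does not guarantee detection when only part of the clone carries the lesion.

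The cost is one derivation rule on data already collected (screening CD5/CD19 flow and leukocyte count), a query to the laboratory on what was scored, and a smaller evaluable cytogenetics set.

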### 9.3. Study Time Periods

Adverse events, concomitant medications, blood product, death, subject disposition, ECOG, laboratory, image data, vital signs, constitutional symptoms, lymph node examination, organ examination, biomarker, and questionnaire data (EORTC QLQ-C30, EORTC QLQ-CLL16, and EQ-5D) will be assigned to the treatment periods defined below. Flag variables indicating the treatment period will be added to these datasets.

**Pre-therapy** is defined as the time prior to the subject's first dose of study treatment for subjects randomized to the ofatumumab arm. For subjects randomized to the "No further treatment (observation)" arm, pre-therapy is defined as the time prior to the subject's randomization date.

**On-treatment** is defined as the time from start date/time of study treatment until the end date/time of the study treatment + 30 days for subjects randomized to the ofatumumab arm. The start date of the on-treatment phase is the date of the first dose of study drug. The end of study treatment is defined as the last dose of planned treatment. For subjects randomized to the "No further treatment (observation)" arm, on-treatment is defined as the time from randomization until the date of entry into follow-up.

There are specific rules to handle the cases where start date/time is equal to start date/time of study treatment or the start date/time is missing for different classes of data sets:

- For interventions and events, including adverse event, concomitant medications, blood product, death, and disposition, i.e., if the date/time is equal to start date/time of study treatment or time is not available and the date is equal to start date of study treatment, the flag will be set to on-treatment. If the start date is missing, and the end date/time is before start date/time of study treatment, the flag will be set to pretreatment. If start date is missing and end date/time is not before the start date/time of study treatment, or both start date and end date are missing, the flag will be set to on-treatment.
- For findings, including ECOG status, laboratory data, imaging data, vital signs, constitutional symptoms, lymph node examination, organ examination, and biomarker if the date/time is equal to start date/time of study treatment, the flag will be set to pre-treatment. If time is not available and the date is equal to start date of study treatment, the flag will be set to pre-treatment. If the date is missing, the flag will be set to on-treatment.

**Post-treatment** is defined as any time beyond the on-treatment period.

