#### 9.3.1. Study Time Periods for Concomitant Medications and Blood and Blood Supportive Care Products

Concomitant Medication and Blood and Blood Supportive Care Product start and end dates will be assigned to study time periods in relation to first dose of study treatment as defined below. The start date references time flag variables and end date reference time

flag variables will be added to the concomitant medications and blood and blood supportive products datasets, respectively.

- **Start relative to treatment:** Assign to 'BEFORE' if start date is prior to study treatment start date or if subject has not taken any study treatment or (start date is missing and end date is before study treatment start date). Else assign to 'DURING' if the start date falls into the on-therapy period as defined above or if subject is ongoing (not all study treatment discontinuation records completed) or start date is missing. Else assign to 'AFTER' if start date is after the on-therapy period.
- **End relative to treatment:** Assign to 'BEFORE' if end date is prior to study treatment start date or if subject has not taken any study treatment. Else assign to 'DURING' if start date falls into the on-therapy period or if subject is ongoing (not all study treatment discontinuation records completed) or (end date is missing and start relative to treatment not 'AFTER'). Else assign to 'AFTER' if start date is after the on-therapy period or (end date is missing and start relative to treatment='AFTER').

Only on-therapy blood and blood supportive care products that start after the start of study treatment are included in the Blood Products and Blood Supportive Care Product summaries. Therefore, for summary tables, include blood and blood supportive care product records where start relative to treatment in ('DURING') and end relative to treatment in ('DURING','AFTER'). All data will be reported in listings.

Concomitant medication start relative to treatment and end relative to treatment flags are used to select data to include in the Concomitant Medication summaries as follows:

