## **12. SAFETY ANALYSES**

Unless otherwise specified, all the safety analyses will be based on the Safety population as defined in Section 6 and summaries will include all events or assessments collected during the study. All the analyses will be performed by treatment arm.

The list of displays for the Safety Analyses is shown in a separate document from the RAP.

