### **12.2. Adverse Events**

All SAEs and AEs regardless of relationship to investigational product will be collected from the first dose of investigational product to 60 days after the last dose of investigational product and will be documented on the eCRF. All SAEs and AEs for subjects not receiving treatment (observation) will be collected for the same duration time (i.e. Visit 1 until 60 days after last visit, up to Visit 14). Only SAEs will be reported from 60 days after the last dose of investigational product or last treatment/observation visit to

the end of the follow-up period. All SAEs regardless of causality will be collected until the end of the follow-up period.

An overview summary of AEs, including counts and percentages of subjects with any AE, AEs related to study treatment, AEs leading to permanent discontinuation of study treatment, AE leading to dose reductions, AEs leading to dose delays/ interruptions, SAEs, SAEs related to study treatment, fatal SAEs, and fatal SAEs related to study treatment will be produced.

A summary of non-serious AEs that occurred in strictly 5% of the subjects or above will be provided (no rounding for the percentage will be used in terms of 5% threshold, e.g., event with 4.9% incidence rate should not be included in this table). The summary will be displayed by SOC and PT.

The relationship between MedDRA SOC, PT, and Verbatim Text will be displayed.

Adverse events (AEs) will be graded according to the CTCAE, Version 4.0. Adverse events will be coded to the preferred term (PT) level using the Medical Dictionary for Regulatory Affairs (MedDRA dictionary).

A summary of number and percentage of subjects with any adverse events by maximum grade will be produced. AEs will be sorted by Preferred term (PT) in descending order of total incidence. The summary will use the following algorithms for counting the subject:

- **Preferred term row:** Subjects experiencing the same AE preferred term several times with different grades will only be counted once with the maximum grade.
- **Any event row:** Each subject with at least one adverse event will be counted only once at the maximum grade no matter how many events they have.

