In addition, the frequency and percentage of AEs (all grades) will be summarized and displayed in two ways: 1) in descending order of total incidence by PT only and 2) in descending order of total incidence by System Organ Classes (SOC) and PT. In the SOC row, the number of subjects with multiple events under the same system organ class will be counted once.

A separate summary will be provided for study treatment-related AEs. A study treatment-related AE is defined as an AE for which the investigator classifies the relationship to study treatment as “Yes”. A worst case scenario approach will be taken to handle missing relatedness data, i.e. the summary table will include events with the relationship to study treatment as ‘Yes’ or missing. The summary table will be displayed in descending order of total incidence by PT only.

All AEs will be listed. Additionally, a listing of subject IDs for each individual AE will be produced.

Adverse events will be summarized and listed separately during the study and up to 60 days after the last dosing.

The following adverse event tables will also be provided for events occurring from the

start of treatment until 60 days after last dosing:

- All adverse events, all serious adverse events (including deaths) for the following:
  - Secondary malignancies
  - Cardiac events
  - Small bowel Obstruction
- All infusion reactions reported as AEs, SAEs and leading to withdrawal
- All infections reported as adverse events, all serious infections reported as adverse events
- All mucocutaneous adverse events, all serious mucocutaneous adverse events
- All decreased neutrophil count/ hemoglobin count/ and platelet count adverse events, all serious decreased neutrophil count/ hemoglobin count/ and platelet count adverse events
- All autoimmune hematologic complication adverse events, all serious autoimmune hematologic complication adverse events
- All tumor lysis syndrome adverse events, all serious tumor lysis syndrome adverse events

The relationship between MedDRA SOC, PT, and Verbatim will be displayed.

Summaries based on the following covariates will be provided for all AEs:

- Gender
- Age: <70 vs. ≥70 years
- Race: White, vs. non-white.

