#### **12.4. Deaths and Serious Adverse Events**

In the event that a subject has withdrawn consent, no data after the withdrawal of consent date from this subject including death is supposed to appear in the database, which should be part of the data cleaning process. All deaths will be summarised based on the number and percentage of subjects. This summary will classify subjects by time of death relative to the last dose of medication (>60 days or ≤60 days) and primary cause of death (disease under study, SAE related to study treatment, or other). A supportive listing will be generated to provide subject-specific details on subjects who died.

All SAEs will be tabulated based on the number and percentage of subjects who experienced the event. SAEs will be summarized up to 60 days after last infusion. Separate summaries will also be provided for study treatment-related SAEs, fatal SAEs and study treatment related fatal SAEs. The summary tables will be displayed in descending order of total incidence OR incidence by PT only.

A study treatment-related SAE is defined as an SAE for which the investigator classifies the relationship to study treatment as “Yes”. A worst case scenario approach will be taken to handle missing data, i.e. the summary table will include events with the relationship to study treatment as ‘Yes’ or missing.

SAEs are included in the listing of all adverse events. Separate supportive listings with subject-level details will be generated for

- Fatal SAEs
- Non-Fatal SAEs.

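### SAP 9.3 ends the on-treatment period by different rules in the two arms and leaves the observation rule undefined, so the blood-product and concomitant-medication tables are not comparable between arms.

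*SAP*

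**What the plan says.** SAP 9.3 assigns records to pre-therapy, on-treatment and post-treatment periods and flags a long list of datasets accordingly. For ofatumumab, "The start date of the on-treatment phase is the date of the first dose of study drug", and the period runs "until the end date/time of the study treatment + 30 days for subjects randomized to the ofatumumab arm". For the observation arm, "on-treatment is defined as the time from randomization until the date of entry into follow-up". Neither the SAP nor the protocol says whether entry into follow-up is the last observation visit, the first follow-up visit or some date between them.

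Adverse events follow another rule. SAP 12.2 has them collected "from the first dose of investigational product to 60 days after the last dose", and both it and Protocol 6.4.8 ask for the same duration in the observation arm, ending 60 days after the last visit.

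The on-therapy period is put to explicit use in SAP 9.3.1 and 10.5. For blood products, "Only on-therapy blood and blood supportive care products that start after the start of study treatment are included"; the concomitant-medication summaries are selected with the same start and end flags. SAP 9.3.1 sets both flags to BEFORE for any subject who took no study drug. The resulting tables, 3.1280 (blood products and supportive care) and 1.4240 (concomitant medications), are in the output lists for both the 280-event analysis and the final analysis.

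**The concern.** A between-arm count of subjects with some event is interpretable only if the two arms are watched for comparable lengths of time. Here one arm's clock is tied to the last infusion and the other's to an administrative transition that the plan does not date. Two programmers could follow the text and produce windows whose imbalance runs in opposite directions.

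The 30-day tail is also about half of one 8-week dosing interval and half of the adverse event window. A medication or blood product that an ofatumumab subject starts on day 45 after the last dose is therefore post-treatment under SAP 9.3, while an adverse event on the same day falls inside the 60-day adverse event tables.

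At stake are the comparability of two descriptive tables, and possibly of the split of progressions into treatment and follow-up in SAP 11.3.2, if that analysis uses the same flag.

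**Working it through.** The plan gives no figure for the length of either window, so there is none to reproduce. The inputs are:

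- Last treatment or observation visit (Visit 14): Week 97 (Protocol Appendix 1).
- First follow-up visit (Visit 15): Week 109 (same table).
- Visit windows: ±7 days for Visits 3-14 and ±14 days in follow-up (same table).
- Ofatumumab tail: 30 days (SAP 9.3). Adverse event tail: 60 days (SAP 12.2, Protocol 6.4.8).
- Assumption: randomization and first dose both fall in Week 1, and the subject attends every visit.

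**Gap between Visit 14 and Visit 15.** (109 - 97) × 7 = 84 days. The SAP's own 168-day limit for the first follow-up assessment (9.2.12) agrees with this: 84 + 56 + 28 = 168. With visit windows the gap runs from 84 - 7 - 14 = 63 to 84 + 7 + 14 = 105 days, so 84 is a nominal value and not a maximum.

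**Nominal on-treatment window for a completer.** Week 1 to Week 97 is (97 - 1) × 7 = 672 days.

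| Arm and reading | Days | Difference from ofatumumab |
|---|---|---|
| Ofatumumab | 672 + 30 = 702 | - |
| Observation, entry = Visit 15 | 672 + 84 = 756 | +54 (54/702 = 7.7%) |
| Observation, entry = Visit 14 | 672 + 0 = 672 | -30 (30/702 = 4.3%) |

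**Early stoppers.** Suppose the last infusion was given 8 weeks before the scheduled visit at which treatment stops. The ofatumumab window closes on day 30 and the visit is on day 56, so it falls 56 - 30 = 26 days outside. In the observation arm the corresponding visit is inside the window if entry into follow-up comes after it.

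**SAP 9.3.1 applied to an untreated arm.** An observation subject has taken no study drug, so both the start flag and the end flag are BEFORE. The blood-product summary requires start = DURING and end = DURING or AFTER, which the subject fails. The concomitant-medication summary requires start = BEFORE or DURING and end = DURING or AFTER; the subject fails on the end flag. Read literally, both tables lose the whole observation arm.

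**The case against.** The strongest reply is that the period flag reaches little. SAP 12 states that, unless otherwise specified, "summaries will include all events or assessments collected during the study". Section 12.2 adds that "Adverse events will be summarized and listed separately during the study and up to 60 days after the last dosing", and 12.4 that "SAEs will be summarized up to 60 days after last infusion". Infections pool treatment and follow-up (12.3). Laboratory, vital sign and ECOG data are shown by scheduled visit, and patient-reported outcomes are modelled over time. No table in the later output lists has on-treatment in its title. All of this stands, and it limits the point to the outputs named above.

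A reader might infer that every safety comparison, or the transfusion endpoint, is distorted. The documents do not support that. SAP 11.2 counts transfusions over the whole study (Table 3.1210); only the separate blood-product table uses the on-therapy window. The PFS censoring rules and the definitions of time to next therapy and overall survival do not use the period either.

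A reader might also infer that observation subjects always have the longer tail, or that early leavers gain a large proportion. The first holds only if entry is Visit 15. The second cannot be calculated, because the plan does not date follow-up entry for someone who stops early. Even on the Visit 15 reading, Appendix 1 footnote 12 limits reporting from day 60 to serious events and their associated medications. For other medications the usable excess is therefore nearer 60 - 30 = 30 days than 54.

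Finally, the BEFORE rule was probably written for subjects assigned to drug but never dosed, and a sensible programmer would not apply it to a whole arm. That is likely, but the text does not say so.

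**Conclusion.** The point holds within these limits. The end rules differ by arm, no visit-based reading of follow-up entry makes the windows equal, and the 30-day tail disagrees with the 60 days used for adverse events. For completers the observation window is between 30 days shorter (-4.3%) and 54 days longer (+7.7%) at nominal visit times, assuming randomization and first dose in Week 1.

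In the two tables that certainly depend on the period, the literal exclusion of untreated subjects matters more than the unequal tail. SAP 11.3.2 may also be affected, but it does not cite the 9.3 definition. No confirmatory result is at risk. This is a correction worth making because it is cheap and the tables concerned are reported by arm.

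**What to change.** - In SAP 9.3, define on-treatment in the same way for both arms: from the safety reference date already set out in SAP 9.2.1 (first dose for ofatumumab, randomization for observation) to 60 days after the last dose or, for observation, the last treatment-phase visit. For completers this gives 672 + 60 = 732 days in each arm and matches the adverse event rule.
- In SAP 9.3.1, for observation subjects, replace the study treatment start date and the condition of having taken no study drug with the safety reference date, so that they stay in the blood-product and concomitant-medication summaries.
- In SAP 11.3.2, state that progression during treatment versus follow-up uses this same period.

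One residual should be acknowledged. If an ofatumumab subject stops at a scheduled visit without an infusion, the anchor is the infusion 56 days earlier. The 60-day tail covers that visit with 60 - 56 = 4 days to spare, but an observation subject's tail starts at the visit itself. The adverse event rule has the same feature.

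The cost is SAP wording and one derivation change. No new data are needed.
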